
It is well known that dietary protein is a powerful transient stimulator of the muscle protein synthetic rate (MPS) (9-11) whereby changes in MPS in response to feeding may be regulated by specific downstream target proteins of mammalian target of rapamycin signaling, such as S6K1, rpS6, and eIF2B (11). A meal deficient in protein, however, does not increase the rate of MPS because a rise in the bioavailability of amino acids does not occur (12, 13). In addition, the source of dietary proteins has been shown to impact postprandial blood levels of amino acids. The concept that certain types of proteins are "fast acting" or "slow acting" has been shown to affect the postprandial profile of amino acids appearing in the systemic circulation (13). Native whey and micellar casein are both dairy proteins that contain a similar amount of essential (EAA), but blood EAA levels increase faster and to a higher level after the consumption of whey protein (13, 14). Differences in gastric emptying, digestion and absorption kinetics between micellar casein and native whey are the underlying factors (13). Nonetheless, micellar casein protein has been shown to protract MPS in humans (15). Despite the significant amount of information gained with respect to both of these protein sources, the effects of combinatorial

Supplementation of a Leucine-Enriched Dairy Protein Blend: Chronic and acute metabolic responses in young men and women

formulations on the postprandial profile of amino acids appearing in the blood is less well known.

Purpose and hypothesis

The primary purpose of this study is to evaluate changes in integrated (day-to-day) rates of myofibrillar MPS in response to the product and a short-term resistance training program in young men and women. A secondary purpose is to assess the acute postprandial skeletal muscle protein signalling response to the ingestion of the product in young men and women. Based on the results of a previous dairy protein bioavailability study (13) and our previous results (17, 18) we hypothesize that training + supplementation will result in greater integrated rate of muscle growth.

Experimental approach

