In a cross-over, randomized controlled trial, 10 healthy young participants (5 men and 5 women) will be recruited to undergo exercise resistance training randomized to habitual diet or habitual diet and supplementation (2 x per training session). For two of the training sessions we will utilize a uni-lateral resistance exercise model to identify the acute effects of exercise and exercise + supplementation on the integrated rate of myofibrillar MPS within subject. This model enhances statistical power and eliminates between-subject differences impacting our outcomes. Throughout the study participants will record their macronutrient dietary intake. In addition, baseline body composition will be assessed with dual-energy x-ray absorptiometry.

Sample size estimate. We have previously detected significant alterations in myofibrillar fractional synthetic rates and lean muscle mass in response to step-reduction, and following the consumption of dietary protein and energy restriction (18-22). As a proof-of-concept investigation we will recruit $n=10$ per group.

METHODS

Body composition will be determined using dual energy x-ray absorptiometry (DXA) scans. The DXA procedures use a small amount of radiation to determine the bodies fat, bone, and lean mass. The procedure takes approximately seven minutes and involves lying still on an open bed while the sensor passes over the body.

Integrated rates of protein synthesis will be assessed with the precursor-product method using ingested deuterium labeled water (70 %D₂O) as we have shown previously (23, 24). Briefly, to increase deuterium (²H) enrichments in total body water to ~1%, participants will consume 4 D₂O doses (0.8ml/kg lean body mass per dose) on the loading day and 1 dose (0.8ml/kg lean body mass) on maintenance days. Total body water ²H enrichment will serve as a surrogate for plasma alanine ²H labeling (24-26). Daily saliva sampling will be continued until the end of the experimental trial to assess precursor pool enrichments. Muscle samples (~40–50mg) will be separated into myofibrillar and sarcoplasmic fractions and processed as previously described (27)

Supplementation of a Leucine-Enriched Dairy Protein Blend: Chronic and acute metabolic responses in young men and women

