Muscle biopsies will be sampled from the *vastus lateralis* using the Bergstrom technique before and after resistance training with either supplementation or habitual diet. Biopsies will be analysed for markers of protein synthesis utilizing Western blotting and PCR in addition to integrated MPS. The molecular mechanisms that underpin MPS in response to stimulation are complex, multifactorial and remain largely unknown. However, what is known is that proteins contained within the Akt-mTORC1-p70S6K1 signaling axis appear key. Thus, we propose to examine how the content of proteins contained within the Akt-mTORC1-p70S6K1 signaling axis change during our intervention. We also will examine changes in the DNA-protein ratio (an indicator of cell size) as well as mRNA expression of myogenin, MAFBx and MuRF1, some of which have been shown to change in response to muscle growth, using real-time PCR. ***Thus, our molecular analysis coupled with the use of the deuterated water methodology provides a mechanism-based clinical approach to study the impact of supplementation on skeletal muscle health.***

Venous Blood Sampling

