Two-way repeated measures ANOVAs with time and treatment as factors will be used to compare differences between supplementation + exercise and habitual diet over the 8 days of resistance training. Where significant interaction is detected, post-hoc test will be applied to locate these differences. Statistical significance is set at $P < 0.05$. Calculations and analyses will be performed using the Prism V.7. and SPSS V.25. software packages.

Knowledge translation

The primary form of knowledge translation from these projects will be via conference presentations, published scientific papers, and press releases. We anticipate at least one major paper to arise from the project described here and at least that number of presentations at National and International meetings from Drs. [name] and [name]. We have a good publication record and would also opt for an online/open access journal or opt to pay an open access fee to allow wider use of our data. In addition, the PI gives at least 1-2 keynote lectures at various conferences both at National and International meetings. Hence, there will be relatively widespread dissemination of the data from these trials. As an adjunct member in the Department of Medicine, Faculty of Health Sciences, the PI is also positioned to present this work via Grand Rounds and other local seminars to clinicians to get information to those who can implement the findings into their practice. There will also be press releases that accompany each manuscript to more widely publicize the findings and garner the interests of clinically-oriented web services such as Web MD, Medscape, The Doctor's Page, and Healthcentral.com. We will also work with the McMaster Knowledge Translational Team, <http://www.mcmaster.ca/cfh/knowledgetranslation.html> - using McMaster PLUS, which is a premium 'literature service' at McMaster University designed to decrease the 'noise-to-signal

Supplementation of a Leucine-Enriched Dairy Protein Blend: Chronic and acute metabolic responses in young men and women

ratio' in articles from clinical journals. This service sends registered physicians e-mail updates with links to articles that are relevant to their discipline.

References

1. Grooper SS, Smith JL (2012). *Advanced Nutrition and Human Metabolism*. Belmont, CA USA: Wadsworth, Cengage Learning

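### With biopsies only before and after training, integrated myofibrillar MPS has one rate per condition, so the planned time-by-treatment interaction does not exist for it

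*Combined protocol and SAP*

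**What the plan says.** Under Purpose and hypothesis, the primary purpose is to "evaluate changes in integrated (day-to-day) rates of myofibrillar MPS in response to the product and a short-term resistance training program". The hypothesis is that training plus supplementation gives the greater integrated rate.

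Under Methods, "Integrated rates of protein synthesis will be assessed with the precursor-product method using ingested deuterium labeled water". There is one loading day, followed by single maintenance doses. On the precursor side, "Daily saliva sampling will be continued until the end of the experimental trial to assess precursor pool enrichments". Biopsies are taken "before and after resistance training with either supplementation or habitual diet" and are also used for blots, PCR and the DNA-protein ratio. The text does not give the number of biopsies, the legs sampled, or where the first biopsy falls relative to the loading day.

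Under Experimental approach, the trial is a cross-over in 10 people, and two sessions use a one-legged exercise model meant to separate the acute effects of exercise, alone and with the supplement, on MPS within the person.

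Under Statistics, "Two-way repeated measures ANOVAs with time and treatment as factors will be used" to compare the two conditions across 8 training days. Post-hoc tests follow only a significant interaction, at P < 0.05. The levels of time are not defined.

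**The concern.** One model is written for two kinds of outcome. Blots, PCR and the DNA-protein ratio have a value at each biopsy, so a before/after pair gives them two time levels. An integrated MPS rate belongs to the interval between two biopsies, so the same pair gives it one value and no time levels.

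If that is the design, the rule for locating differences cannot be applied to the outcome that the trial is mainly about. The analyst would have to choose the MPS contrast during analysis, with only 10 participants and no contrast named in advance. If there are more biopsies, the rule can be computed, but it asks whether the supplement effect changes over time. The hypothesis asks whether the rate is greater with the supplement.

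**Working it through.** **Inputs.** 10 participants and a cross-over of 2 conditions (Experimental approach); precursor-product rates and before/after biopsies (Methods); time-by-treatment ANOVA with an interaction gate, P < 0.05 (Statistics). The plan gives no effect size, standard deviation or power, so it has no figure of its own to reproduce here.

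**Step 1: rates per condition.** For one interval,

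rate = (E_after − E_before) / (mean body-water enrichment × elapsed time),

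where E is protein-bound ²H-alanine enrichment in muscle. Hence k rates need k + 1 muscle samples. One before/after pair gives 2 − 1 = 1 rate per condition, 2 per participant and 2 × 10 = 20 in all. Daily saliva refines the denominator but adds no muscle sample, so it adds no rate.

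**Step 2: degrees of freedom.** With n = 10, 2 treatments and t time levels: time t − 1; treatment 1, with error 9; interaction t − 1, with error 9(t − 1).

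| Biopsies per condition | Outcome | t | Time df | Treatment df (error) | Interaction df (error) |
|---|---|---|---|---|---|
| 2 | MPS rate | 1 | 0 | 1 (9) | 0 (0) |
| 2 | Blots, PCR, DNA-protein ratio | 2 | 1 | 1 (9) | 1 (9) |
| 3 | MPS rate | 2 | 1 | 1 (9) | 1 (9) |
| 4 | MPS rate | 3 | 2 | 1 (9) | 2 (18) |

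The design matrix confirms the first row: 20 rates and rank 11 (10 participants plus 1 treatment term), with nothing left for time or interaction.

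**Step 3: a second leg.** If both legs were biopsied, each participant would have 2 legs × 2 conditions = 4 rates. The added factor is leg. Time still has one level.

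**Step 4: several on-treatment intervals.** Let the habitual-diet rates be a₁ and a₂, and let the supplement add δ to both. The interaction is [(a₂ + δ) − (a₁ + δ)] − (a₂ − a₁) = 0 for any δ. The treatment effect averaged over intervals is (δ + δ)/2 = δ. A constant benefit is therefore invisible to the interaction and fully visible to the treatment contrast.

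**Step 5: what the direct contrast can detect.** Assuming 80% power and a two-sided 5% level (neither is stated in the plan), the paired comparison with 9 error df detects a mean difference of about 1.00 standard deviations of the within-person differences (noncentral t; 0.89 by normal approximation). A period term leaves 20 − 10 − 1 − 1 = 8 error df. The critical t rises from 2.26 to 2.31 and the detectable difference from 1.00 to 1.01, taking 5 participants in each order.

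**The case against.** The strongest reply is that the premise is not fixed by the text. No biopsy count is given, and the schematic, a natural place for biopsy days, is not visible. Three biopsies per condition would restore an interaction with 1 and 9 degrees of freedom. If one interval came before treatment, for example because labelling began before the first biopsy, an interaction would even carry the treatment effect. This stands, so the point is conditional on the Methods text. That text describes no such interval, and nothing in it defines time for MPS.

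A second reply is that the ANOVA contains a treatment main effect. That is true, and it is why the trial's central comparison survives. But the plan does not name that effect as the MPS test, and its only stated route to locating differences runs through the interaction.

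Three stronger readings are tempting, and the documents do not support them:

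- **That MPS cannot be analysed at all.** The treatment contrast is estimable with the biopsies described.
- **That no untrained rate is measured, so the training-response aim must go.** The one-legged model is meant to isolate the effect of exercise on MPS within the person, and a rested leg may be sampled. The text does not say either way.
- **That raw muscle enrichment would be analysed and would carry labelling differences into the supplement effect.** The Methods specify the precursor-product method with precursor sampling, which excludes that analysis.

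**Conclusion.** The concern holds conditionally. On the Methods text as written, MPS has one rate per participant per condition (per leg, if both are sampled), and the interaction used to locate differences has 0 degrees of freedom for it. This rests on reading the text as one biopsy pair per condition; the schematic could change that. The second part does not depend on the count: with several on-treatment intervals, an interaction gate still does not test for a greater integrated rate.

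The fault lies in the stated analysis. The between-condition contrast that matches the hypothesis can be tested with the planned data. Whether a response to training itself can be claimed is open, because the text does not say which legs are biopsied.

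**What to change.** In the Statistics section:

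- Make the primary MPS test the within-person difference in rate, supplementation plus training minus habitual diet plus training. Compute each rate from its own biopsies and its own mean body-water enrichment. Include a period term for the cross-over and use no interaction gate.
- If there are several on-treatment intervals, test the treatment effect averaged over them and make interval-by-treatment secondary. If a pre-treatment rate exists, adjust for it.
- Keep the time-by-treatment ANOVA for blots, PCR and the DNA-protein ratio.
- Claim a response to training itself only if a rested-leg or untrained rate is measured under the one-legged model, and analyse it with a leg factor.

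In the Methods, state the biopsy days, legs and labelling intervals. If the schematic shows more biopsies than the text, reconcile the biopsy and Statistics passages with it.

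The cost is a short rewording and one error degree of freedom for period (9 to 8). It needs no extra biopsy or participant.

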A needle will be inserted into a forearm vein by a physician or a medically trained and certified member of the laboratory group, and a blood sample will be drawn (~5 mL or 1 teaspoons). The discomfort of this procedure is transient and is very similar to having an injection by a needle, e.g. when donating blood. Upon removal of the needle any discomfort should subside. During the course of the experiment, five blood draws will occur. In this experiment, the total blood taken is ~50 mL, which is 1/10th of the blood removed during a donation to a blood bank. This amount of blood loss is not enough to affect your physical performance in any way. After each blood sample has been taken pressure will be placed on the site in order to minimize bleeding and facilitate healing. The insertion of a needle for blood sampling is a common medical practice and involves few risks if proper precautions are taken. The needles are inserted under completely sterile conditions; however, there is a theoretical risk of infection. There is a chance of internal bleeding if adequate pressure is not maintained upon removal of the needle. This may cause some minor discomfort and could result in bruising/skin discoloration, which could last up to a few weeks. In very rare occasions, trauma to the vessel wall could result in the formation of a small blood clot, which could travel through the bloodstream and become lodged in a smaller vessel. However, we have never experienced such a complication after several thousand blood draws.

Resistance training will be composed of CrossFit style exercises individually customized to each participant (28). Prior to trial initiation, participants will report to the laboratory for familiarization of these types of exercises. In addition, for uni-lateral lower body resistance training sessions participants will perform 3 sets of leg press and leg extension exercises to volitional failure. 3-5 repetition maximum testing will be performed during the familiarization session to estimate 1-RM values for the leg press and leg extension exercises to allow for the determination of loads equal to approximately 80-90% 1-RM. For each exercise 6-10 repetitions/set will be completed.

Supplementation of a Leucine-Enriched Dairy Protein Blend: Chronic and acute metabolic responses in young men and women

Schematic overview of study design. DXA, dual-energy X-ray absorptiometry.

Statistics

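### Does the mismatch between five ~5 mL blood draws and a ~50 mL total call for a change to the plan?

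*Combined protocol and SAP*

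**What the plan says.** The Venous Blood Sampling section describes a forearm needle insertion at which "a blood sample will be drawn (~5 mL or 1 teaspoons" is the stated volume. It then gives the count and the total: "During the course of the experiment, five blood draws will occur. In this experiment, the total blood taken is ~50 mL". The total is put on a familiar scale, "which is 1/10th of the blood removed during a donation to a blood bank", and the participant is reassured: "This amount of blood loss is not enough to affect your physical performance in any way". The section also says "After each blood sample has been taken pressure will be placed on the site".

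Other sections say where the study's measurements come from. In Methods, the deuterium precursor is followed in saliva: "Daily saliva sampling will be continued until the end of the experimental trial to assess precursor pool enrichments". The muscle biopsy paragraph covers the tissue measures: "Biopsies will be analysed for markers of protein synthesis utilizing Western blotting and PCR in addition to integrated MPS". The purpose statement names myofibrillar protein synthesis and muscle signalling. Statistics describes a two-way repeated measures ANOVA with time and treatment as factors. Neither names a blood variable. Blood amino acids appear only in the background. The experimental approach is a cross-over in 10 participants.

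**The concern.** Three figures given within a few sentences of each other cannot all be taken literally. Each volume also has its own gloss, a teaspoon for the sample and a tenth of a donation for the total, so neither looks like a simple mistyped digit.

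The procedure is invasive and the wording addresses the participant. The possible readings differ in burden: half the stated blood, twice the stated number of needle insertions, or twice the stated volume at each insertion. A reader would normally settle this from the assay's requirements, but the readable text names no assay for the blood. If an outcome depended on these samples, a doubtful count or an unknown analyte would leave that outcome undefined. That possibility is what made the point worth checking.

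A side question was whether "As a proof-of-concept investigation we will recruit $n=10$ per group" conflicts with a cross-over of 10 people.

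**Working it through.** **Inputs, all from Venous Blood Sampling:** volume per sample v = 5 mL; number of draws n = 5; stated total T = 50 mL; stated share of a donation = 1/10.

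**1. Reproduce the stated total.** n × v = 5 × 5 = 25 mL. The stated figure is 50 mL, and 50 / 25 = 2. It does not reproduce.

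**2. Check the donation comparison.** The implied donation is 50 / (1/10) = 500 mL. The comparison therefore agrees with the stated total. The multiplied total would be 25 / 500 = 0.05, or 1/20th.

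**3. See whether rounding explains the gap.** If a teaspoon is taken as 4.93 mL (an assumption, not in the documents), 5 × 4.93 = 24.65 mL. Rounding does not help.

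**4. Find what would close the gap.**

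| Reading | Arithmetic | Total |
|---|---|---|
| Five draws, one 5 mL sample each | 5 × 5 | 25 mL |
| Five draws, two 5 mL samples each | 5 × 2 × 5 | 50 mL |
| Five draws, 10 mL each | 5 × 10 | 50 mL |
| Five draws in each of two cross-over periods | 2 × 5 × 5 | 50 mL |

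The second row keeps every printed figure and needs only an unstated detail, namely two samples per draw. The fourth fits the design, but the sentence counts five draws over the whole experiment, so the count would need rewording. The text does not say which row is meant.

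**5. Trace what depends on the blood.**
- Integrated protein synthesis: the precursor is read from saliva and the product from muscle. Methods says that body-water enrichment stands in for plasma alanine labelling, so this calculation needs no plasma.
- Signalling proteins, DNA-protein ratio and mRNA: biopsy.
- Body composition: DXA.
- Sample size: justified by earlier work and proof-of-concept status, with no blood input.
- Statistics: the factors are time and treatment, and no blood variable is listed.

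Nothing in this list takes blood volume or number of draws as an input. Whichever row of the table is right, the results of the stated analyses are the same.

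**6. The side question.** In a cross-over, 10 people each receiving both conditions give 10 observations per condition. Read with group meaning condition, the sample size sentence agrees with the 10 participants in the experimental approach. It has no bearing on blood sampling.

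**The case for a change.** The strongest case for acting is that the inconsistency is certain, concerns needle insertions in volunteers, and costs a few words to remove. An ethics board reading the section cannot tell whether five or ten insertions are planned. The section lists infection, bruising and clot as risks of the procedure, so the count is not trivial to a participant. The five-per-period explanation is a conjecture, and the text as printed contradicts it.

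All of that stands as a reason for the sponsor to reconcile the wording with its draw schedule. It does not amount to a statistical defect. Reconciliation would bring the text into line with whatever is already scheduled. It would not alter an estimate, a test or a comparison.

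The complaint that no use is stated for the blood is weaker. The readable text indeed names no assay. However, the study title refers to acute metabolic responses, the background ends on blood amino acid profiles after mixed formulations, and the secondary purpose is a postprandial response. The schematic and another figure are not visible in the copy reviewed and may label the draws. One Methods sentence would fill this gap. Listing blood under Purpose and Statistics would presume that it is an outcome, which the documents do not say; it could equally serve screening or description.

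**Conclusion.** The arithmetic criticism is correct: 25 mL by multiplication against about 50 mL stated, a factor of two, and 1/20th against 1/10th of the implied donation. The documents do not show which figure, or which missing detail, is responsible.

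No change to the plan follows. The slip is confined to descriptive text, and no stated endpoint, sample size or analysis uses the numbers. Every reading in the table totals 25 or 50 mL, so participants would not give more blood in total than the section already states. The one practical uncertainty is the number of insertions, five or ten, which the study's draw schedule should settle.

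This conclusion assumes that the blood supplies no outcome beyond those named in the readable text, and that the schematic does not introduce one. Even if it did, the mismatch in volumes would remain a matter of wording. The sample size phrase is consistent on its natural reading and needs nothing.

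### For the before/after biopsy markers, the only stated decision rule is the time-by-treatment interaction, a valid but imprecise test with 10 people; adjusting for the before biopsy would usually be tighter

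*Combined protocol and SAP*

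**What the plan says.** All references are to the combined protocol and SAP.

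- **Experimental approach.** The design is a randomised cross-over: "In a cross-over, randomized controlled trial, 10 healthy young participants (5 men and 5 women) will be recruited". The sample-size paragraph in the same section adds "As a proof-of-concept investigation we will recruit $n=10$ per group", with no effect size, standard deviation or power.
- **Methods, muscle biopsy paragraph.** Biopsies are taken "before and after resistance training with either supplementation or habitual diet". They supply the integrated synthesis rate and also a set of markers: protein content in the Akt-mTORC1-p70S6K1 pathway, the DNA-protein ratio, and "mRNA expression of myogenin, MAFBx and MuRF1".
- **Statistics.** "Two-way repeated measures ANOVAs with time and treatment as factors will be used to compare differences between supplementation + exercise and habitual diet". The follow-up rule is "Where significant interaction is detected, post-hoc test will be applied to locate these differences". The significance level is 0.05.

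No covariate, baseline adjustment, period term or measurement scale is named for any outcome.

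**The concern.** The before biopsy of each condition enters the planned test only by being subtracted. Subtracting it in full suits a before-difference that strongly predicts the after-difference. If it predicts weakly, subtraction mainly adds assay and sampling noise. A cross-over contrast has already removed stable differences between people, so what is left to predict may be modest.

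At stake is the chance of seeing a real supplement effect on the mechanism markers. Follow-up comparisons depend on a significant interaction, so an imprecise interaction test makes it more likely that a real effect is reported as absent. These samples are invasive and come from only 10 people.

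**Working it through.** **The plan's own figure.** The stated n=10 cannot be reproduced, because no effect size, SD, correlation or power is given. The check therefore compares the precision of candidate analyses at n=10.

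**Inputs.**
- From the documents: 10 participants, each measured under both conditions (I read the per-group figure as 10 per condition in the cross-over); significance level 0.05, taken as two-sided because an ANOVA F test with one numerator degree of freedom is two-sided.
- Assumed: one before and one after biopsy per condition; equal variance *s*² of the within-person supplement-minus-habitual difference before and after; a true effect of 1 *s*; and r, the correlation between the before-difference and the after-difference, shown over a range.

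**Step 1: what the interaction tests.** In a 2 × 2 within-person layout the interaction F is the squared paired t on (after − before on supplement) − (after − before on habitual diet). A numerical check on generated data gave F = 0.6386 and t² = 0.6386 on 1 and 9 df.

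**Step 2: variances, in units of *s*²/n.**
- Interaction: 2(1 − r).
- After-only paired difference: 1.
- Baseline-adjusted (intercept from regressing the after-difference on the before-difference): (1 − r²) × (n − 2)/(n − 3) = (1 − r²) × 8/7 at n=10.

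The adjusted-to-interaction ratio is therefore (8/7)(1 + r)/2. It equals 1 when 1 + r = 1.75, so r = 0.75. Because the adjusted test also has 8 df rather than 9, confidence-interval widths break even slightly earlier, at about r = 0.7.

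**Step 3: results at n=10, no period term.** Interval-width ratios come from simulation (40,000 trials per setting). Powers agree between simulation and a noncentral-t calculation to within about a point.

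| r | Var. interaction | Var. adjusted | Ratio | 95% CI width ratio | Power: interaction | Power: adjusted | Power: after-only |
|---|---|---|---|---|---|---|---|
| 0 | 2.00 | 1.14 | 0.57 | 0.76 | 52% | 74% | 80% |
| 0.3 | 1.40 | 1.04 | 0.74 | 0.87 | 66% | 78% | 80% |
| 0.5 | 1.00 | 0.86 | 0.86 | 0.94 | 80% | 85% | 80% |
| 0.6 | 0.80 | 0.73 | 0.91 | 0.97 | 88% | 90% | 80% |
| 0.7 | 0.60 | 0.58 | 0.97 | 0.995 | 95% | 95% | 80% |
| 0.8 | 0.40 | 0.41 | 1.03 | 1.03 | 99% | 99% | 80% |

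At r=0 the noncentral-t value for the interaction is 51.4%; simulation gave 51.8%. Type I error was about 5% for all three analyses.

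**Step 4: with a period term.** Interaction versus adjusted power becomes 50% vs 72% (r=0), 65% vs 76% (0.3), 79% vs 83% (0.5) and 94% vs 93% (0.7).

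**Step 5: does the treatment main effect rescue the plan?** It averages the before- and after-differences, so its expectation is half the effect, with variance (1 + r)/2. Its standardised size is 0.5/√((1 + r)/2) = 1/√(2(1 + r)), against 1/√(2(1 − r)) for the interaction. For r ≥ 0 it is never the stronger test.

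**The case against.** **The biopsy schedule is not confirmed.** The biopsy paragraph gives no count or timing, and the study schematic is not in the text available here. The one-leg exercise sessions and the acute signalling aim could each change the schedule. If one before biopsy serves both conditions, the interaction collapses to the after-difference, the proposed covariate is zero for everyone, and the point does not apply. With more than two time points the figures above no longer hold. This stands as a condition. A separate pair per condition is the most natural reading, but a reader should not take it as established.

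**The gain is not all due to adjustment.** A reader might infer from the r=0 row that using the baseline recovers 22 points of power. It does not. There the before-difference carries no information, and the gain comes from no longer subtracting it. At r of about 0.3 or less an after-only paired test does slightly better (80% against 74–78%). Adjustment is preferred because r is unknown: after-only stays at 80% when the other two reach 95%, and the interaction falls to about 52% when r is 0.

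**The planned test is valid.** This is correct. A reader might infer a false-positive problem or a biased estimate from the choice of test, but type I error is at its nominal level. Nor does the text say that the interaction is the only thing computed: "Two-way repeated measures ANOVAs with time and treatment as factors will be used", and an ANOVA also prints main effects. The narrower statement holds: the interaction is the only result to which a decision is attached.

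**The scale.** A reader might infer that the plan commits to raw-scale analysis and loses a further known amount of power that way. The Statistics section does not mention scale, so neither inference is supported. The log scale is recommended here for interpretation as a ratio, without any power claim.

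**The outcomes are not primary.** True. The primary purpose is the integrated myofibrillar synthesis rate, which this point does not touch, and the study describes itself as proof-of-concept.

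**Conclusion.** The point holds as an optional improvement in precision for secondary and mechanistic markers. If each condition has its own before and after biopsy, the interaction test at n=10 has about 75% more variance than the adjusted one at r=0 (2.00/1.14), 35% more at r=0.3 (1.40/1.04) and 17% more at r=0.5 (1.00/0.86). There is no useful difference at about 0.7, and adjustment is slightly worse above about 0.75; simulated intervals are about 5% wider at r=0.9, or 7% with a period term.

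The size rests on r, which the documents do not give. Under a simple random-subject model r is 0, which makes low to moderate values plausible, but it remains an assumption. The result also assumes equal before and after variances and no carry-over into the second before biopsy. Confidence is moderate because the schedule cannot be checked here.

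**What to change.** 1. State in the Methods whether each condition has its own before biopsy. If it does not, leave the analysis of these markers as it is on this point.
2. If it does, add to Statistics, for each blot, PCR and DNA-protein marker: take logs, form each participant's supplement-minus-habitual difference after training, and regress it on the same participant's difference before training. Include period if the model uses it, coded symmetrically (for example ±1 by sequence).
3. Test the intercept as the treatment effect. Do not mean-centre the before-difference, because the intercept must refer to a before-difference of zero. Report the back-transformed estimate as a ratio with a 95% CI.
4. Keep the time-by-treatment ANOVA as a supportive display.

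The cost is a few lines of text and one degree of freedom (8 rather than 9 without a period term), with no gain, or a loss of about one point of power with a period term, at r of about 0.7. It needs no extra samples or participants, and SPSS, already named in the plan, can fit it.
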